2.1.2. Estimands for Continuous Secondary Endpoints

Only discontinuation of the investigational product will be considered as an intercurrent event to define the estimands for this study. The endpoint of change from baseline (Δ) in Patient Global Assessment of Disease (PGA) will be used as an example in defining the estimands. Estimand 4 will be used for other continuous secondary endpoints by appropriately substituting the endpoint. Estimand 5 will be used only for the Type I error controlled continuous secondary endpoints as supportive analyses.

Estimand 4:

This estimand of Δ PGA at Week 16 is a hypothetical estimand. It estimates the treatment effect as if the intercurrent event of discontinuation of investigational product prior to Week 16 has not occurred. This includes the following four attributes:

- Population: Subjects who have active AS;
- Variable: Δ PGA at Week 16;
- Intercurrent event: Only data collected before the intercurrent event of discontinuation of the investigational product prior to Week 16 are included, ie, On-Drug data (see [Section 9.1](#));
- Population-level summary: The mean difference in Δ PGA between tofacitinib 5 mg BID and placebo at Week 16.

Estimand 5:

This estimand of Δ PGA at Week 16 is supportive to Estimand 4 and is a treatment policy estimand. It estimates the effect regardless of treatment adherence. It includes the following four attributes:

[figure not shown]
- Population: Subjects who have active AS;
- Variable: Δ PGA at Week 16;
- Intercurrent event: The intercurrent event of discontinuation of the investigational product prior to Week 16 is not considered here for data exclusion. Data collected after the discontinuation of the investigational product prior to Week 16 (ie, off-drug data) are also included, ie, On-Study data are used (see [Section 9.1](#));
- Population-level summary: The mean difference in Δ PGA between tofacitinib 5 mg BID and placebo at Week 16.

The difference between Estimand 5 and Estimand 4 is that Estimand 5 disregards treatment adherence and includes the additional data collected after the intercurrent event of discontinuation of the investigational product prior to Week 16, ie, On-Study data are used. (see [Section 9.1](#)).

2.2. Study Design

This is a phase 3, multicenter, randomized, double-blind, placebo-controlled efficacy and safety study designed to compare tofacitinib to placebo in subjects with active AS. An estimate of approximately 480 AS subjects will be screened globally in order that approximately 240 eligible subjects (120 per arm) will be randomized in a 1:1 ratio to tofacitinib 5 mg BID (twice daily) or matching placebo BID. [Figure 1](#) shows the schematic of the study design.

Figure 1. Schematic of Study Design

Abbreviations: AS = Ankylosing Spondylitis; ASAS20 = Assessment of SpondyloArthritis International Society 20; bDMARD = biological disease-modifying antirheumatic drug; BID = twice daily; IR = inadequate responder; N = number of subjects; PBO = placebo; TNFi = tumor necrosis factor inhibitor.

The duration of participation for eligible subjects will be approximately 56 weeks. This will include a screening period of approximately 30 days, a 16-week double-blind treatment period, a 32-week open-label treatment period and a 28-day follow-up period. During the 16-week treatment period subjects will visit the clinic every two weeks (± 3 days) until the Week 4 visit and then every 4 weeks (± 7 days) until the completion of Week 16. At the Week 16 visit all subjects will be assigned to open-label tofacitinib and will visit the clinic every two months (± 7 days) until Week 48. Subjects will then return to the clinic for a Follow-up visit approximately 28 days after the Week 48 visit. There will be a total of 2 planned analyses conducted when all applicable subjects have completed their Week 16 and Week 48 (including follow-up) visits, respectively. The first analysis will be conducted when all applicable subjects have completed their Week 16 visit. The investigators, subjects, and sponsor study team will remain blinded to the first 16 weeks of treatment assignment through the entire duration of trial until database release. Randomization will be stratified by prior treatment history: (1) bDMARD-naïve and (2) Tumor Necrosis Factor inhibitor-inadequate responder (TNFi-IR) or bDMARD Use (Non-IR). Subjects who had prior bDMARD use (Non-IR) will be eligible to participate in the study after washout and will be included in the "TNFi-IR or bDMARD Use (Non-IR)" stratum. Approximately 80% of the subjects will be bDMARD-naïve (designed as Stratum "bDMARD-naïve"), and the other approximately

20% of subjects who had an inadequate response to at least one but not more than 2 TNF inhibitors or who had prior bDMARD use (Non-IR) (designed as Stratum "TNFi-IR or bDMARD Use [Non-IR]"). All subjects will have an inadequate response to at least 2 NSAIDs. An inadequate response to NSAID or TNFi treatment is defined as having a treatment related adverse event or lack of response to NSAID or TNFi treatment that was administered in accordance with its labeling recommendations.

3. ENDPOINTS AND BASELINE VARIABLES: DEFINITIONS AND CONVENTIONS

3.1. Primary Endpoint

- ASAS20 response at Week 16 (see [Section 9.2.1](#)).

3.2. Secondary Endpoints

3.2.1. Key Secondary Endpoint

- ASAS40 response at Week 16 (see [Section 9.2.1](#)).

3.2.2. Other Secondary Endpoints

- ASAS20 response at all other time points (Weeks 2, 4, 8, 12, 24, 32, 40, and 48) (see [Section 9.2.1](#));
- ASAS40 response at all other time points (Weeks 2, 4, 8, 12, 24, 32, 40, and 48) (see [Section 9.2.1](#));
- Change from Baseline (Δ) in Ankylosing Spondylitis Disease Activity Score using C-Reactive Protein (Δ ASDAS_{CRP}) at all time points (Weeks 2, 4, 8, 12, 16, 24, 32, 40, and 48) (see [Section 9.2.4](#));
- Δ in High Sensitivity C-Reactive Protein (Δ hsCRP, mg/L) at all time points (Weeks 2, 4, 8, 12, 16, 24, 32, 40, and 48);
- Δ in Ankylosing Spondylitis Quality of Life (Δ ASQoL) at Weeks 16 & 48;

A total score is calculated by summing the 18 items. The total score ranges from 0 to 18, with higher values indicating more impaired health-related quality of life.

- Δ in 36-Item Short Form Health Survey Version 2 (Δ SF-36v2), Acute at Weeks 16 & 48;

This survey yields 10 endpoints: 8 general health domains: physical functioning, role limitations due to physical health, bodily pain, general health perceptions, vitality, social functioning, role limitations due to emotional problems, and mental health. These domains can also be summarized as physical and mental component summary scores (see [Section 9.2.7](#)).

- Δ in Bath Ankylosing Spondylitis Metrology Index (Δ BASMI) and its 5 components (Δ in Lateral Spinal Flexion, Tragus-to-Wall Distance, Lumbar Flexion [as measured by Modified Schober's test score], Maximal Intermalleolar Distance, and Cervical Rotation) at all time points (Weeks 2, 4, 8, 12, 16, 24, 32, 40, and 48) (see [Section 9.2.3](#));
- Δ in Functional Assessment of Chronic Illness Therapy-Fatigue (Δ FACIT-F) (Total Score, Experience Domain Score, and Impact Domain Score) at all time points (Weeks 2, 4, 8, 12, 16, 24, 32, 40, and 48);

This instrument has 13 items that assess fatigue. Instrument scoring yields a range from 0 to 52 for Total Score, with higher scores representing better subject status (less fatigue). For Experience Domain Score, range is 0-20; for Impact Domain Score, range is 0-32 (see [Section 9.2.9](#)).

- Δ in Patient Global Assessment of Disease (Δ PGA) at all time points (Weeks 2, 4, 8, 12, 16, 24, 32, 40, and 48). PGA is one of the 4 ASAS20/ASAS40 components;
- Δ in Patient Assessment of Spinal Pain (two numerical rating scales [NRS]: Δ in Nocturnal Spinal Pain and Total Back Pain, respectively) at all time points (Weeks 2, 4, 8, 12, 16, 24, 32, 40, and 48). Total Back Pain is one of the 4 ASAS20/ASAS40 components;
- Δ in Bath Ankylosing Spondylitis Functional Index (Δ BASFI) at all time points (Weeks 2, 4, 8, 12, 16, 24, 32, 40, and 48);

This instrument consists of 10 questions. BASFI is the average of these 10 scores and it ranges from 0 to 10, with higher scores indicating greater functional limitation. If the number of missing scores is ≤ 3 , then BASFI is calculated based on the average of the remaining non-missing scores, otherwise if the number of missing scores is >3 , then BASFI is considered missing (Ramiro et al., 2014).¹ BASFI is one of the 4 ASAS20/ASAS40 components.

- Δ in Inflammation at all time points (Weeks 2, 4, 8, 12, 16, 24, 32, 40, and 48);

Inflammation is one of the 4 ASAS20/ASAS40 components, which is the average of the answers to questions 5 & 6 of BASDAI (see [Section 9.2.2](#)). If answer to one of the two questions is missing, the other non-missing answer will be used as inflammation. If both answers are missing, inflammation is considered missing (Ramiro et al., 2014).¹

- ASAS 5/6 response at all time points (Weeks 2, 4, 8, 12, 16, 24, 32, 40, and 48) (see [Section 9.2.1](#));
- ASAS Partial Remission response at all time points (Weeks 2, 4, 8, 12, 16, 24, 32, 40, and 48) (see [Section 9.2.1](#));

- Δ in Bath Ankylosing Spondylitis Disease Activity Index (Δ BASDAI) at all time points (Weeks 2, 4, 8, 12, 16, 24, 32, 40, and 48) (see [Section 9.2.2](#));
- BASDAI50 response at all time points (Weeks 2, 4, 8, 12, 16, 24, 32, 40, and 48) (see [Section 9.2.2](#));
- ASDAS_{CRP} Clinically Important Improvement response at all time points (Weeks 2, 4, 8, 12, 16, 24, 32, 40, and 48) (see [Section 9.2.4](#));
- ASDAS_{CRP} Major Improvement response at all time points (Weeks 2, 4, 8, 12, 16, 24, 32, 40, and 48) (see [Section 9.2.4](#));
- ASDAS_{CRP} Inactive Disease response at all time points (Weeks 2, 4, 8, 12, 16, 24, 32, 40, and 48) (see [Section 9.2.4](#));
- Δ in Maastricht Ankylosing Spondylitis Enthesitis Score (Δ MASES) at all time points (Weeks 4, 8, 12, 16, 24, 32, 40, and 48) (see [Section 9.2.6](#));
- Δ in extra-articular involvement (Specific Medical History and peripheral articular involvement [as assessed by Swollen Joint Count (44) (Δ SJC[44])]) at all time points (Weeks 2, 4, 8, 12, 16, 24, 32, 40, and 48) (see [Section 9.2.5](#));
- Δ in Spinal Mobility: Chest Expansion at all time points (Weeks 2, 4, 8, 12, 16, 24, 32, 40, and 48);

The chest expansion (cm) is measured as the difference between maximal inspiration and expiration. Two attempts will be performed and the better (ie, larger) of the two attempts will be utilized for data analysis.

- Δ in EuroQol-5D Health State Profile – 3 Level Version (Δ EQ-5D-3L) (5 Dimensions: Mobility, Self-Care, Usual Activities, Pain/Discomfort and Anxiety/Depression, “Your own health state today” [Δ EQ-VAS], and EQ-5D-3L Utility score based on United Kingdom (UK) weights) at Weeks 16 & 48 (see [Section 9.2.8](#));
- Δ in Work Productivity & Activity Impairment (Δ WPAI) Questionnaire: Spondyloarthritis (4 subscale scores in range of 0-100%) at Weeks 16 & 48 (see [Section 9.2.10](#)).

The 4 subscales are (1) percent work time missed due to health problem, (2) percent impairment while working due to health problem, (3) percent overall work impairment due to health problem, and (4) percent activity impairment due to health problem.

3.3. Tertiary/Exploratory Endpoints

- [REDACTED]
- Fluorescence Activated Cell Sorting (FACS) analysis of lymphocyte subsets;
- Ankylosing Spondylitis HealthCare Resource Utilization Questionnaire (AS-HCRU and Δ AS-HCRU Self-Rating of Job Performance at Work which is question 14 with range of 0-10) at Weeks 16 & 48.

3.4. Baseline Variables

Baseline value of an endpoint is the value obtained on Day 1 (ie, Baseline visit) or prior before the first dose of the investigational product. A subject's prior treatment history at randomization, defined by two categories: "bDMARD-naïve" and "TNFi-IR or bDMARD Use (Non-IR)" (see [Section 3.4.1](#)), which is used as a factor for stratified randomization, is described in more detail below and also in [Appendix Section 9.11](#).

3.4.1. Stratification Factor

Subjects will be stratified by prior treatment history (strata of "bDMARD-naïve" and "TNFi-IR or bDMARD Use [Non-IR]") at randomization. The stratum derived from data collected on prior medications taken and on the reasons for their discontinuation in the clinical database will be used for analysis. Specifically, prior medications taken before Day 1 collected on the Prior and Concomitant Medications DMARD CRF pages (bDMARDs subcategory) will be used to derive the strata. An inadequate response to a medication is defined when its discontinuation was due to either adverse event or lack of efficacy (see [Appendix Section 9.11](#) for additional details to derive this stratification factor). For the primary endpoint of ASAS20 at Week 16 and the key secondary endpoint of ASAS40 at Week 16 only, a sensitivity analysis may need to be performed using the stratum from the randomization system (if there are differences between that from the randomization system and that derived from the clinical database) (see [Section 6.1.2](#) and [Section 6.2](#)).

3.5. Safety Endpoints

- Incidence and severity of Adverse Events (AE);
- Clinical laboratory tests, vital signs, physical examination and 12-lead ECG parameters;
- Fluorescence Activated Cell Sorting (FACS) analysis of lymphocyte subsets.

In addition to standard safety displays, a 3-tier approach will be used to summarize AEs. Under this approach, AEs are classified into 1 of 3 tiers.

- Tier-1 events: These are pre-specified events of clinical importance and are maintained in a list in the product's Safety Surveillance Review Plan. This is a set of AEs of special interest that has been identified for the tofacitinib compound.

- Tier-2 events: These are events that are not Tier-1 but are “common” (ie, occurring ≥ 4 subjects in any treatment group). A Medical Dictionary for Regulatory Activities (MedDRA) Preferred Term (PT) is defined as a Tier-2 event if there are at least 4 subjects in any treatment group reporting an event.
- Tier-3 events: These are events that are neither Tier-1 nor Tier-2 events.

The 3 tiers are mutually exclusive. Tier-3 events will be included in standard safety displays and not separately displayed in specific Tier-3 tables.

4. ANALYSIS SETS

Below are descriptions of the Analysis Sets defined for this study.

4.1. Full Analysis Set

The full analysis set (FAS) will include all subjects who were randomized to the study and received at least one dose of the randomized investigational product (ie, tofacitinib or placebo). The primary efficacy population for this study is defined by the FAS of subjects. Subjects will be analyzed in the treatment groups as they are randomized. If a subject is treated but not randomized, then the subject will be excluded from the FAS. A narrative will be provided for this subject in the clinical study report (CSR).

Continuous and ordered-categorical (analyzed as continuous) endpoints for which change or percent change from Baseline is the measure to be analyzed, would require that a subject has a Baseline value and at least one post-baseline value to be included in the FAS for that endpoint. It is anticipated that there should be little bias due to excluding subjects with no Baseline value since the missingness mechanism is likely to be missing completely at random (MCAR) (Rubin, 1987).² Excluding a subject with no post-baseline would likely cause a more favorable estimate of the mean change from Baseline for that endpoint for the treatment group in which that subject was assigned. However, it is anticipated that very few subjects will be excluded for this reason minimizing any potential bias.

4.2. Per Protocol Analysis Set

The Per-Protocol (PP) analysis set will exclude all subjects from the FAS who had a protocol deviation (see [Section 4.2.1](#) below) thought to have a material impact on the primary efficacy analysis. The PP analysis set will be used in conjunction with Estimand 1 as a supportive analysis for the primary endpoint of ASAS20 at Week 16 and the key secondary endpoint of ASAS40 at Week 16 (see [Section 2.1.1](#)).

4.2.1. Protocol Deviations

Only protocol deviations that are thought to affect the primary efficacy endpoint of ASAS20 at Week 16 and the key secondary endpoint of ASAS40 at Week 16 will be considered in defining the PP analysis set. The following sections describe protocol deviations that will lead to subject exclusion from the PP analysis set. It is possible that unexpected deviations will arise, becoming known only after the study has been active for a long period of time; hence more deviations may be added to the list at a later date. As of this writing, the protocol deviations that will define the PP analysis set can all be found in [Section 4.2.2](#) and [Section 4.2.3](#) below.

The list of subjects along with the protocol deviation that excludes them from the PP analysis set will be finalized prior to the treatment unblinding for the Week 16 analysis and put into the Trial Master File (TMF).

4.2.2. Deviations Assessed Prior to Randomization

Exceptions to the inclusion or exclusion criteria are not expected to occur; but any subject who fails meeting any of the following protocol inclusion criteria will be excluded from the PP analysis set.

- Subjects who failed to meet the Modified New York Criteria for Ankylosing Spondylitis (1984) at screening. The AS diagnosis at screening is recorded on the Case Report Form (CRF) page for primary diagnosis. A subject who did not have this CRF page filled out will be considered having this exclusion criterion for PP analysis set met.
- Subjects who had BASDAI score <4 or back pain score (BASDAI Question 2) <4 assessed at either screening or Baseline (ie, Day 1) visit. The BASDAI CRF pages at screening and Baseline will be used to check this condition.
- Subject who failed to meet the criteria of at least 2 NSAIDs-IR (see definition of inadequate response to NSAID in [Appendix Section 9.10](#)).
- Subjects who failed to meet the criteria of:
 - Being naïve to prior bDMARD, or
 - Having an inadequate clinical response or intolerance due to treatment-related AE to at least 1, but not more than 2 approved TNFi's (ie, 1 or 2 TNFi-IR) or having bDMARD Use (Non-IR).

[Appendix Section 9.11](#) provides more details on how to check these criteria and to derive the stratification factor.

Full lists of DMARDs and NSAIDs can be found in [Section 9.6](#).

4.2.3. Deviations Assessed Post-Randomization

These specific classes of protocol deviations will be assessed post randomization up to Week 16 only:

- Subjects who were randomized but took or received incorrect treatment other than the randomized treatment for the entire duration from Baseline through Week 16. This will be checked manually since there is no CRF page for this condition.
- Subjects who had <80% compliance on the investigational product's tablets on 2 consecutive visits (ie, 2 dosing periods) for the period from Baseline through Week 16. The investigational product compliance (%) will be derived from the total number of doses actually taken divided by the total number of doses expected to take per dosing period as recorded in Oral Dosing CRF page. Both the randomized treatments (ie, tofacitinib and placebo) will be taken into account.
- Subjects who were dosed with rescue medication for AS on the preceding day or the same day of the primary endpoint assessment at the Week 16 study visit. The rescue medication is recorded on the Concomitant Medications – Rescue Medications CRF page.

Each subject's presence on the list of exclusion from the PP analysis set means that there was at least one deviation for that subject.

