5.4. Investigational Product Supplies

5.4.1. Dosage Form(s) and Packaging

During the double-blind treatment period, blinded tofacitinib and matched placebo will be provided as tablets for oral administration. The tofacitinib 5 mg tablets or placebo tablets will be supplied in bottles and labeled according to local regulatory requirements. The investigational product will be labeled in such a manner that the subject and study staff will be unable to determine from the dispensed packaging to which treatment sequence the subject is assigned. All blinded investigational product will be collected at the Week 16 visit and subjects will receive new investigational product as part of the open-label portion of the study at the Week 16 visit and will receive the first dose of open-label investigational product in the clinic. At the Week 16 visit, all subjects will receive tofacitinib 5 mg tablets supplied in containers and labeled according to local regulatory requirements. Supplies will be labeled as appropriate for this two-arm placebo-controlled, double-blind trial and the open-label treatment period.

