5.4.2. Preparation and Dispensing

The investigational product will be dispensed using an IRT drug management system at each visit from Baseline to Week 40 (excluding Week 2). A qualified staff member will dispense the investigational product via unique container numbers in the bottles provided, in quantities appropriate for the study visit schedule. The subject/caregiver should be instructed to

maintain the product in the bottle provided throughout the course of dosing and return the bottle to the site at the next study visit.

The investigational product will be packaged and labeled in such a manner that the subject and study staff will be unable to determine from the dispensed packaging to which treatment arm the subject is assigned during the double-blind treatment period. At study visits sufficient investigational product will be dispensed to complete dosing until the next scheduled visit. The amount of investigational product dispensed at each visit must be recorded. At study visits the subject must return all investigational product and the amount of investigational product returned will be recorded to account for all dispensed investigational product.

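### The per-protocol rule for wrong treatment acts only when the error lasts all 16 weeks, so a subject on the other arm's drug for one to three of the four dispensing periods stays in the set

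*SAP*

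**What the plan says.** SAP 4.2 builds the per-protocol set by removing from the full analysis set (FAS) subjects with a deviation "thought to have a material impact on the primary efficacy analysis". SAP 4.2.3 lists three post-randomization deviations, assessed up to Week 16:

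- Wrong treatment: subjects who "took or received incorrect treatment other than the randomized treatment for the entire duration from Baseline through Week 16". On the source of this information the SAP adds: "This will be checked manually since there is no CRF page for this condition".
- Compliance below 80% on two consecutive visits, calculated as the "total number of doses actually taken divided by the total number of doses expected to take per dosing period". The bullet closes with "Both the randomized treatments (ie, tofacitinib and placebo) will be taken into account".
- Rescue medication on the day of the Week 16 assessment or the day before.

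SAP 4.2.1 says that the current list is wholly contained in 4.2.2 and 4.2.3, that unexpected deviations may be added later, and that the list of excluded subjects is final before unblinding for the Week 16 analysis.

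On supply, Protocol 5.4.2 has product "dispensed using an IRT drug management system at each visit from Baseline to Week 40 (excluding Week 2"), by unique container number. Protocol 5.4.1 adds: "All blinded investigational product will be collected at the Week 16 visit". Product dispensed at Week 16 is open-label.

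**The concern.** Product is handed out one dispensing period at a time, so a wrong container would naturally put a subject on the wrong treatment for part of the 16 weeks. The rule ignores part-period errors of any length. A tofacitinib subject who took placebo in the last period before the endpoint, or a placebo subject who took tofacitinib then, would be counted as per protocol in the randomized arm.

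Such errors are foreseeable. Protocol 8.3.4.1 defines medication errors and how to record them, and Table 3 in SAP 6.1.2 has a medication-error category among the reasons for stopping product. SAP 6.1.2 justifies Supportive Analysis 2 by the possibility that the FAS contains deviations that matter for the primary endpoint. If subjects who took the other arm's drug stay in the per-protocol set, the analysis does not do that job for this deviation.

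**Working it through.** **Design figure, as an anchor for the rates.** Protocol 9.1 assumes 40% on placebo, a 20-point difference, 120 per arm and two-sided 5%, and states about 89% power. With the unpooled variance of SAP 5.2.1.1:

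- SE = √(0.4×0.6/120 + 0.6×0.4/120) = √0.004 = 0.0632
- Power = Φ(0.20/0.0632 − 1.96) = Φ(1.20) = 88.5%

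The pooled version gives 87.7%. Both agree with the stated figure to within 2 points, so 40% and 60% are used below.

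**Number of blinded periods.** Dispensing at every visit from Baseline except Week 2 gives Baseline and Weeks 4, 8 and 12. Week 16 starts the open-label supply. There are therefore four blinded periods of about four weeks each.

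**The wrong-treatment rule applied literally.**

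| Wrong periods (of 4) | Weeks on wrong treatment | Excluded as written | Excluded if one full period suffices |
|---|---|---|---|
| 1 | 4 | No | Yes |
| 2 | 8 | No | Yes |
| 3 | 12 | No | Yes |
| 4 | 16 | Yes | Yes |

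**Whether another listed rule catches the case.** The compliance formula counts doses. A wrong bottle taken in full gives doses taken / doses expected = 100%. The sentence about both randomized treatments says that tofacitinib and placebo tablets both count; it does not compare the tablets with the assignment. The rescue bullet concerns other drugs. The bullets in SAP 4.2.2 concern entry criteria. None of them applies.

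**Comparison with the neighbouring rules.** A tofacitinib subject who takes fewer than 80% of tablets in two consecutive periods is removed. So is a subject with one rescue dose the day before Week 16. A tofacitinib subject given placebo for three of four periods, and so without active drug for 12 weeks, is kept.

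**Size.** The documents give no misdispensing rate, so this part is conditional.

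- If k of 120 placebo subjects respond at 60% instead of 40%, the difference is understated by k/120 × 20 points. For k = 1 this is 0.17 points.
- Assume, only to show a range, independent errors at 0.1% to 1% per dispensing. P(at least one in four) = 1 − (1 − p)⁴ = 0.4% to 3.9%, or about 1 to 9 of 240 subjects.
- Under the same assumption, an error in the last period affects 120 × p = 0.12 to 1.2 subjects per arm. Even if each responds fully like the other arm, the effect is at most 1.2 × 0.17 = 0.2 points per arm.
- Three or more wrong periods: 240 × [4p³(1 − p) + p⁴] is about 0.001 subjects at p = 1%. All four: p⁴ = 10⁻¹² to 10⁻⁸ per subject.

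If errors are independent, the rule as written would almost never operate, and the cases it misses are nearly all single-period errors. Systematic kit errors could give longer runs, but the documents offer nothing from which to estimate them.

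**The case against.** The strongest reply is that nothing decisive rests on this set. The primary analysis uses the FAS as randomized, and the decision rules in SAP 5.1 contain no per-protocol criterion. A reader might infer that the gap threatens the primary result or could produce a false positive. The documents do not support that: mixing arms generally pulls a difference toward zero, and only a supportive analysis is touched. This part of the reply stands in full.

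A reader might also infer that long exposures, up to 12 of 16 weeks, are to be expected. The rule would indeed keep such a subject, but there is no error rate in the documents, and under independent errors such runs are practically absent. This limit stands too.

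The closing phrase of bullet 1 may have been meant as the window of observation, since the compliance bullet uses a similar phrase that way. That is possible, so it should not be read as a deliberate choice to keep crossed-over subjects. But the lead-in already sets the window at Week 16, and the phrase as placed qualifies the wrong treatment. It needs rewording on either reading.

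Finally, SAP 4.2.1 allows deviations to be added before unblinding. That clause is for unexpected deviations, whereas wrong treatment is already listed with an explicit threshold. The clause offers a route to the fix but does not supply the missing rule.

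**Conclusion.** The point holds as a minor one. The wrong-treatment rule keeps subjects who had the other arm's drug for one to three of four dispensing periods, no other listed rule removes them, and this does not fit the standard that SAP 4.2 sets for the set. The effect is confined to Supportive Analysis 2 for ASAS20 and the matching ASAS40 analysis. Its direction is generally toward no difference. Its size is unknown; the figure of about 0.17 points per placebo subject rests on the design rates of 40% and 60%, 120 per arm, and a full switch to the other arm's response rate.

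**What to change.** In SAP 4.2.3, bullet 1, replace the phrase requiring the error to last the whole 16 weeks with: *for at least one full dispensing period between Baseline and Week 16*. Another threshold would also serve, since one wrong bottle in Weeks 0 to 4 followed by 12 weeks of correct treatment is arguable as material. It should be fixed before the Week 16 unblinding and should at least cover the last period before the endpoint.

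Name the sources. IRT container assignments alone are not enough, because they show what was assigned and not necessarily what was handed over or taken. Add the drug accountability records (Protocol 5.7) and the medication error page of the CRF (Protocol 8.3.4.1). An unblinded group should make the comparison so that the study team stays blinded. Reconcile the SAP's remark that no CRF page exists for this condition with Protocol 8.3.4.1.

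The cost is a reworded bullet and one check of existing records before unblinding. The per-protocol set may lose a few more subjects.
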